## Part II: Data and Safety Monitoring Board or Committee

- *When appropriate, attach a description of the DSMB.*
- *Provide the number of members and area of professional expertise.*
- *Provide confirmation that the members of the board are all independent of the study.*

Given that study activities involve no more than risks encountered in daily life (increased time spent walking by healthy, working individuals), the study has not convened a DSMB.

## 16. WITHDRAWAL OF SUBJECTS

- *Describe anticipated circumstances under which subjects will be withdrawn from the research without their consent*
- *Describe procedures for orderly termination*
- *Describe procedures that will be followed when subjects withdraw from the research, including partial withdrawal from procedures with continued data collection.*

Concern for withdrawal of study participants is likely only relevant to participants engaged in the 10-week personalized trial. Circumstances under which participants will be withdrawn from the research without their consent include failure to maintain protocol adherence, repeated failure to respond to text prompts or self-reported adverse side effects of increased walking. A participant will not be randomized to receive the (8-week) intervention protocol until he/she has demonstrated at least 80% adherence to Fitbit monitoring (activity recorded at least 10 hours/day during the two-week baseline period of the personalized trial).

Participants will be notified in the informed consent of the possibility of being removed from the study before the 8-week intervention period due to adherence issues.

Participants who fail to maintain protocol adherence or who deviate from the protocol will be contacted by a member of the study team with a reminder of the study protocol, and warning that this may impact their continued study eligibility. Once a protocol deviation has been repeatedly recorded, the Principal Investigator will determine the participant's continued eligibility in the study, with consultation of the safety monitor if needed. If it is determined that the participant will be withdrawn from the study, the participant will be notified by the research team via email and phone call. The participant will stop receiving notifications and BCT prompts, and will be sent instructions to un-link their Fitbit device. Participants who are withdrawn due to low adherence during the intervention portion will be able to keep their Fitbit.

Should a participant choose to withdraw from research, they will be instructed to email the study email address ([[contact]](mailto:[contact])), an e-mail account monitored by IRB-approved members of the research team. Participants will be contacted by a member of the research team confirming their study withdrawal, and to answer any questions they may have. The participant will stop receiving notification and survey prompts, and will be sent instructions to un-link their Fitbit device. Data collection will stop the business day the letter or email is received. All data up until the receipt date of the letter will be included in the research study.

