#### **4. OBJECTIVE(S)/SPECIFIC AIMS AND HYPOTHESES**

- *A concise statement of the goal(s) of the current study.*
- *The rationale for and specific objectives of the study.*
- *The goals and the hypothesis to be tested should be stated.*

The specific aims of the study include:

-Eliciting and incorporating participant feedback in the development of required content and study procedures for implementation of a personalized, virtual

interventional trial to enhance low-intensity walking using behavioral change techniques

- Determine the feasibility of conducting a virtual, randomized control trial using participant selected behavioral change techniques
- Examine the novel individual-level heterogeneity of treatment effect made possible by the crossover, personalized trial design, and pool results across patients to efficiently estimate the overall efficacy of the four behavioral change techniques in increasing low-intensity walking by 2,000 steps, 5 days per week.
- Assess the relationship between individual behavior change techniques and walking self-efficacy.
- Elicit participant attitudes and opinions toward using Personalized Trials to help inform their personal wellness strategy

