## 10. ENDPOINTS

- *Describe the primary and secondary study endpoints*
- *Describe any primary or secondary safety endpoints*

This study is a feasibility pilot whose primary objective is to assess the acceptability, scalability of implementation and participant satisfaction with a personalized trial methodology using behavior change techniques to promote low-intensity physical activity. Secondary endpoints include pooling personalized trial results to assess efficacy of BCTs utilized to promote walking behavior.

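### Removal for poor engagement after randomisation also ends step collection and leaves no stated route to the final satisfaction survey

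*Combined protocol and SAP*

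**What the plan says.** Section 16 (Withdrawal of Subjects) lists these grounds for removal without the participant's consent: "failure to maintain protocol adherence, repeated failure to respond to text prompts or self-reported adverse side effects of increased walking". Removal is not immediate. The study team first sends a reminder and a warning, and then "Once a protocol deviation has been repeatedly recorded, the Principal Investigator will determine the participant's continued eligibility in the study". No numerical threshold is given. Once someone is removed, "The participant will stop receiving notifications and BCT prompts, and will be sent instructions to un-link their Fitbit device".

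Removal after randomisation is clearly foreseen: "Participants who are withdrawn due to low adherence during the intervention portion will be able to keep their Fitbit". The template instruction at the head of the section asks authors to cover withdrawal procedures, "including partial withdrawal from procedures with continued data collection". The text describes no such arrangement. For voluntary withdrawal, Section 16 keeps the data collected up to the date of notice. It has no matching sentence for removal by the team.

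Section 10 sets the primary objective: to "assess the acceptability, scalability of implementation and participant satisfaction with a personalized trial methodology". Section 4 also aims to "pool results across patients to efficiently estimate the overall efficacy of the four behavioral change techniques". Sections 9 and 11 send the overall satisfaction survey, with the individual report, at the end of the ten weeks or on completion. Section 12 specifies GEE for steps. It gives no analysis set, no rule for missing days and no handling of removed participants.

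**The concern.** In a feasibility pilot, a participant who stops answering prompts or wearing the tracker during a technique is giving evidence on acceptability. Section 16 treats that behaviour as a reason to end both the intervention and the measurement. Two things are at stake.

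- **Satisfaction.** The final survey is tied to the end of the trial. If it goes only to completers, satisfaction is summarised without the people removed for disengaging.
- **Steps.** Whether later blocks are observed depends on engagement in earlier ones. Unweighted GEE generally needs missingness to be unrelated to outcome, given the model's covariates. If the less engaged also gain fewer steps, the pooled change from baseline can be too high.

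**Working it through.** **No planned figure to reproduce.** Section 12 chooses 60 participants by judgement. The documents give no withdrawal rate, effect size or SD, so every input below except the 60 participants and the 2-week block structure is an assumption.

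**Step 1: who is still observed.** Suppose a share q of the 60 is disengaged and gains nothing, the engaged gain 1 unit, and a disengaged participant is removed with probability h at each of the three block changes.

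- Number starting block 4 = 60 × [(1−q) + q(1−h)³]
- Engaged share of block 4 = (1−q) / [(1−q) + q(1−h)³]
- Pooled effect weighted by available blocks = 4(1−q) / Σ[(1−q) + q(1−h)^k], k = 0 to 3; with full follow-up it is 1−q

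For q = 0.2 and h = 0.25, (1−h)³ = 0.422. The bracket is 0.8 + 0.2 × 0.422 = 0.884, so 60 × 0.884 = 53.1 start block 4, and the engaged share is 0.8/0.884 = 0.905. The sum over blocks is 3.2 + 0.2 × 2.734 = 3.747. The pooled effect is 3.2/3.747 = 0.854 against 0.800, an excess of 6.8%.

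| q | h | Start block 4 | Engaged share, block 1 to 4 | Excess, pooled | Excess, block 4 |
|---|---|---|---|---|---|
| 0.1 | 0.1 | 58.4 | 0.90 to 0.925 | 1.4% | 2.8% |
| 0.2 | 0.25 | 53.1 | 0.80 to 0.905 | 6.8% | 13% |
| 0.4 | 0.25 | 46.1 | 0.60 to 0.78 | 14.5% | 30% |
| 0.4 | 0.5 | 39.0 | 0.60 to 0.92 | 27% | 54% |

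**Step 2: size in steps, by estimator.** A simulation used 60 participants, a baseline and four 14-day blocks. The true mean gain was 500 steps/day, with between-person SD 800 and day-to-day SD 2,500. Each person's gain was constant across blocks. The chance of removal after blocks 1 to 3 fell with that gain (logit slope 0.5 to 1.0 per SD). Bias in steps/day:

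| Pooling method | 10% withdrawn | 20% | 30% |
|---|---|---|---|
| Weighted by available blocks | 20-39 | 41-76 | 56-105 |
| GEE, exchangeable correlation (assumed 0.8-0.9; between-person SD 2,500) | 9-18 | 18-35 | 22-46 |
| Per-person effect first, then averaged | about 0 | about 0 | about 0 |

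The first row is 20/500 = 4% to 105/500 = 21% of the assumed effect. The last row is near zero because everyone contributes block 1 and each person's gain is held constant. If gains changed over time, that protection would not be guaranteed. If removal is unrelated to gain, the bias is nil for all three. The sampling SD of the block-weighted estimate is about 140-145 steps/day.

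**Step 3: contrasts between techniques.** These were simulated with random order, an engaged effect of 1,000 steps and q = 0.2 (true mean 800). With equal removal after every technique (h = 0.25), all four show about 854, so the contrasts are unbiased. If removal follows only one technique (h = 0.5), that technique shows about 801 and the others about 843, a false gap of about 42. At q = 0.4 the figures are 599 and 666, a gap of 67.

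**The case against.** A reader might infer more than the documents support.

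- **That non-engagement disappears from the data.** It does not. Each removal follows recorded deviations and can be counted. The safety monitor reviews participation and attrition monthly (Section 15), and the two-weekly surveys exist up to removal. What is lost is what comes after. The monthly review is oversight, though, not a stated endpoint.
- **That removal is automatic.** It is a case-by-case decision by the investigator.
- **That the primary result is inflated.** Section 10 names acceptability, scalability and satisfaction. It defines no adherence rate and no denominator, so there is no stated rate to be inflated.
- **That later blocks are seen mainly in responders because of this rule.** No withdrawal rate is given, and the 80% baseline adherence screen already selects engaged people. Only an increasing share can be claimed.
- **That comparisons between techniques are biased.** Random order protects them unless removal differs by technique.

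The step bias also depends on the estimator. Averaging per-person effects first is a natural way to pool N-of-1 results, and it gives about zero here. Even the largest pooled value, about 105, is below one sampling SD, in a pilot whose efficacy endpoint is secondary. All of this stands and limits the size of the point. It does not supply the missing survey route, the missing statement on data before removal, or continued step capture.

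It is also fair that continued capture recovers little from people removed for not wearing the tracker, and that unprompted blocks are not exposure to the technique. For that reason such data belong in a sensitivity analysis.

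**Conclusion.** The point holds in a limited form. Followed as written, Section 16 cuts off steps because of poor engagement, and the plan does not say how removed participants reach the final satisfaction survey. The survey gap bears on the primary objective and needs no numerical assumption, although that removed participants are less satisfied is plausible rather than documented.

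The effect on the pooled comparison with baseline is conditional. It is about 20-105 steps/day too high on a true 500 if estimates weight by available blocks or days, low responders are removed more often, and 10-30% are withdrawn. It is about zero or nil under the alternatives shown in the working. Bias between techniques needs removal that differs by technique. An inexpensive change to the wording is worthwhile before randomisation starts, because steps not captured cannot be recovered later.

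**What to change.** - **Section 16.** Separate stopping prompts from stopping data collection. A participant withdrawn for low adherence after randomisation stays linked for passive Fitbit capture to week 10 and is offered the end-of-trial satisfaction survey, unless they decline. State that data up to removal are kept, as is already said for voluntary withdrawal.
- **Sections 10 and 12.** Report retention and adherence with everyone randomised as the denominator, counting adherence removals as non-adherent in their remaining blocks. Keep the analysis of prompted blocks, and beside it run a sensitivity analysis that uses steps after removal under the assigned technique schedule.
- **Section 14.** The file linking device to participant is to be destroyed when an individual's participation ends. For these people, define that point as the end of passive capture.

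The grounds for removal can stay as they are, and withdrawals for adverse effects are not addressed here.

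**Cost.** Protocol and consent wording. The tracker is already issued, and these participants keep it. Those removed for not wearing it will give little passive data, and unprompted blocks will dilute the sensitivity estimate.

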receive up to four text message prompts per day. They will complete a measure of self-efficacy (i.e. confidence in their ability to walk without stopping) and a ‘satisfaction with BCT’ survey once every two weeks. At the end of their trial, participants will receive a satisfaction survey and a summary of their observed data to help them learn more about their responses to the four behavioral change techniques and to inform investigators as to the feasibility of N-of-1 study design for future research and clinical applications.

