### **Rationale for Selecting Four Behavioral Change Interventions as a Personalized Trial for Increasing Low Intensity Physical Activity in Older Adults**

Guidelines and recommendations focus on increasing physical activity for older adults, but adherence to recommendations remains low. This is despite the fact that any increase in physical activity is associated with benefit (LIFE trial). Increasing physical activity meets all of our criteria for selection as a use case as outlined in our umbrella grant: it has high public health burden, high heterogeneity of therapy response, and is high priority for a Personalized Trial approach as determined by previously interviewed clinicians and patients. This instance will adapt our personalized, virtual trial platform to testing the efficacy of four behavioral change techniques consistent with theory (Lally & Gardner, 2013) and randomized clinical trials (Lally et al., 2010). This pilot test will enable us to expand our personalized, virtual trial platform of behavioral interventions. Of note, it is possible that personalized trials of behavioral change techniques could eventually be conducted at the direct-to-consumer level.

Without development of innovative platforms for conducting Personalized Trials, with within-participant randomization to eligible wellness management options, patients and clinicians cannot obtain the objective data they need to empirically choose the optimal precise therapy. Scientists may be able to use Personalized trials to better understand the uniqueness of responders versus non-responders. Should this study demonstrate scalable implementation, acceptability and satisfaction with this methodology amongst participants, it will be a critical step in broadening the application and utilization of this methodology to promote wellness behaviors.

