## 9. STUDY TIMELINES

- *Describe the duration of an individuals participation in the study*
- *Describe the duration anticipated to enroll all study subjects*
- *The estimated date of study completion*

The initial phases of study participation will involve either a single session via a virtual interaction (electronic meeting, 1:1 interview or electronic correspondence) or remote evaluation of study message content and frequency over the course of five days. The last study phase will involve a total of 10 weeks of study participation: activity tracking using a Fitbit activity monitor for 10 weeks, and

responding to behavior change strategy prompts and surveys delivered via text message to a secure link for 8 weeks. At the end of the 10 week intervention period, a report containing the individual's responsiveness to each BCT will be sent to the participant, along with a satisfaction survey.

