#### Intervention Delivery

This pilot study will use text messages to deliver four behavioral change techniques identified in Michie et al.’s (2011) paper which identified those BCTs associated with influencing change in physical activity behavior. These BCTs were updated to align with current BCT definitions using Michie et al.’s (2013) Taxonomy of Behavioral Change Techniques. A list of BCTs is provided as an appendix to this protocol. Participants will also receive **bi-weekly surveys** to assess their satisfaction with the given BCT and walking self-efficacy. BCTs will be provided to participants in a randomized crossover design with each BCT delivered individually in one of four 2-week blocks. The order in which participants receive BCTs will be randomized with the randomization order determined by the study

statistician. Prior to BCT delivery (i.e. every two weeks) participants will be sent information/BCT descriptions the day before they start their new BCT so that they understand the differences between the four BCTs for their personalized trial. For instance, BCT descriptions may include:

BCT Name	Definition	Sample Text Message Prompt
Goal Setting Behavior	Set or agree on a goal defined in terms of behavior to be achieved	Set the goal of being more active today. Record your goal
Action Planning	Prompt detailed planning of performance of behavior (must include a setting frequency, duration, and intensity)	“It’s Tuesday. Walk 2,000 steps from 10am -11am this morning.”
Self-Monitoring of Behavior	Establish a method for person to monitor and record their number of active periods based on their Fitbit	“It’s time to check your FitBit dashboard and view how active you have been today.”
Feedback on Behavior	Monitor and provide informative or evaluative feedback on performance of the behavior (e.g. form, frequency, duration, intensity)	“You met your goal yesterday. You walked 2,000 steps more than baseline.”

Participants may receive additional text messages to those outlined above with important reminders to sync their data as needed.

Upon completion, participants in the personalized trials phase will receive an individual report that demonstrates their walking responses in relation to their assigned BCTs and a satisfaction survey to obtain feedback about their personalized trials experience.

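### Satisfaction with the personalised-trial method, part of the primary objective, is surveyed only at the end, and voluntary withdrawers are not asked

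*Combined protocol and SAP*

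**What the plan says.** **Objective.** Section 10 states that the "primary objective is to assess the acceptability, scalability of implementation and participant satisfaction with a personalized trial methodology". Section 4 lists a related aim: "Elicit participant attitudes and opinions toward using Personalized Trials to help inform their personal wellness strategy".

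**When the method is surveyed.** Three places describe the survey, and all put it at the end:
- Section 2: "At the end of their trial, participants will receive a satisfaction survey and a summary of their observed data".
- Section 9: after the 10 weeks, the individual report "will be sent to the participant, along with a satisfaction survey".
- Section 11, Intervention Delivery: on completion, the report is accompanied by "a satisfaction survey to obtain feedback about their personalized trials experience".

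**The other survey.** During the intervention, a survey every two weeks serves "to assess their satisfaction with the given BCT and walking self-efficacy" (Section 11).

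**Withdrawal.** For voluntary withdrawal, Section 16 states: "The participant will stop receiving notification and survey prompts". Collection ends on the working day the notice arrives, and data up to that date are kept. For participants removed by the investigator, the same section stops notifications and technique prompts and does not mention surveys.

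**Analysis.** Section 12 plans a step-count analysis. It gives no analysis set, denominator or missing-data rule for satisfaction.

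**The concern.** The people who choose to leave a ten-week programme of texts and device wear may hold a different view of it from those who stay. Under this plan they are not asked about the method. Keeping their data up to the withdrawal date does not help, because the survey comes later.

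The protocol puts weight on the result. Section 3 says: "Should this study demonstrate scalable implementation, acceptability and satisfaction with this methodology amongst participants, it will be a critical step in broadening" the use of this methodology. Section 2 adds that the pilot should help decide whether the design can be used widely. A figure from those who stayed answers a narrower question. It is too high if leavers are less satisfied and about right if they are equally satisfied, and the study as planned could not tell which. Opinions not sought at exit are hard to recover afterwards.

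**Working it through.** **Step 1: who is asked about the method.** Setting the sections side by side for randomised participants:

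| Participant | Asked about the technique (bi-weekly) | Asked about the method |
|---|---|---|
| Completes | Yes (Section 11) | Yes (Sections 2, 9, 11) |
| Withdraws voluntarily before the end | Only until withdrawal | No: survey prompts and collection stop (Section 16) |
| Removed before the end | Not stated after removal | Not stated (Section 16) |

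The bi-weekly survey is a proxy. It concerns one technique rather than the trial method, and it is absent for anyone who leaves before the first one.

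**Step 2: what the plan's figures allow.** Section 12 gives 60 participants as a feasibility choice (elsewhere up to 60). It states no precision target, dropout rate, satisfaction measure or threshold, so there is no calculation to reproduce and no bias to estimate.

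**Step 3: illustration.** Assumptions, none from the documents: satisfaction is yes/no, all completers answer, about 90% of completers are satisfied, and 6, 12 or 18 of the 60 are lost. Let x be the number known to be satisfied and u the number without an answer.

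- Lower bound = x/60
- Upper bound = (x + u)/60
- Width = u/60

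| u | Completers satisfied | Lower | Upper | Width (points) |
|---|---|---|---|---|
| 6 | 49/54 = 90.7% | 49/60 = 81.7% | 55/60 = 91.7% | 10 |
| 12 | 43/48 = 89.6% | 43/60 = 71.7% | 55/60 = 91.7% | 20 |
| 18 | 38/42 = 90.5% | 38/60 = 63.3% | 56/60 = 93.3% | 30 |

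The width depends only on u, not on the assumed 90%. If 4 completers also fail to answer in the second row, u = 16 and the width is 16/60 = 26.7 points.

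**Step 4: direction.** With u = 12 and L of the leavers satisfied, the completer figure differs from the all-randomised figure by 43/48 − (43 + L)/60:
- L = 12: −2.1 points (completer figure too low)
- L = 9: +2.9
- L = 6: +7.9
- L = 0: +17.9

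**Step 5: what exit answers would buy.** If 6 of the 12 leavers answer the same yes/no question and 3 are satisfied, the bounds become (43 + 3)/60 = 76.7% to (43 + 3 + 6)/60 = 86.7%. The width halves from 20 to 10 points.

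**The case against.** **Other sources partly cover this.** The safety monitor reviews participation and attrition monthly (Section 15), the bi-weekly surveys reach people before they leave, and mock participants comment on the acceptability of procedures (Section 2). These bear on acceptability and scalability. None records what a randomised leaver thinks of the method, and Section 12 treats the preliminary phases as descriptive only.

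**Losses may be few and the bias modest.** The 80% adherence run-in (Section 11) and the $100 paid on completion (Sections 6 and 22) plausibly limit loss after randomisation. Sampling error is also large in a pilot. For 43/48 the exact (Clopper-Pearson) 95% interval is 77.3% to 96.5%, and the all-randomised rate falls below it only if 3 or fewer of the 12 leavers are satisfied: 46/60 = 76.7%, against 47/60 = 78.3% with 4. For 49/54 the interval is 79.7% to 96.9%, and even the worst case of 81.7% lies inside. This stands as a reason for moderate wording. It does not remove the gap, because the interval describes chance variation among those asked and says nothing about those not asked.

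**An early-exit answer is not the same measure.** The survey is paired with the report and follows all four techniques. This stands, and it is why a single pooled rate would be wrong.

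**Stronger readings that the documents do not support.** A reader might infer that removed participants are also excluded. Section 16 is silent on surveys for them, and its different wording for the two groups even allows the reading that they still receive one. A reader might also infer that the satisfaction figure will be overstated. Nothing in the documents shows that leavers are less satisfied.

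**Conclusion.** The concern holds for voluntary withdrawers on the plain text: the method is surveyed only at the end, and their survey prompts and data collection stop before that. For removed participants the plan is unclear rather than excluding. The primary satisfaction result would therefore come without those who chose to leave, and it may be too favourable if they are less satisfied.

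The size is unknown. The only general statement is that the uncertainty over 60 randomised is the number without an answer divided by 60. The figures of 10, 20 and 30 points rest on assumed losses of 6, 12 and 18 and a yes/no reading of satisfaction. Satisfaction is one of three parts of the primary objective, and this is a feasibility pilot, so the point is a correctable gap worth fixing and not a fatal flaw.

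**What to change.** **Section 16.** Amend the voluntary-withdrawal text so that the existing electronic survey is offered once, optionally, as part of the exit contact. State the same for removed participants. Omit items that do not apply, such as those on the final report or on techniques not received. Require no reason for leaving, since Section 17 promises that none is needed. Change the consent form if its wording on stopping collection requires it.

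**Section 12.** Report the numbers randomised, completing and answering. Report satisfaction separately for completers and early leavers. Give best- and worst-case bounds over all randomised, not one pooled rate, which would mix two versions of the survey and, with 60 as the denominator, count non-responders as not satisfied. The bounds need an overall satisfaction item common to both versions.

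**Cost.** A small protocol amendment and possibly a consent change. No new contact is needed: Section 16 already has the team contact people who withdraw and notify those removed by email and phone. It does add an optional request to employees who are leaving. Exit response will be incomplete, so the bounds remain necessary, and the headline figure may look less favourable.
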